At each post-baseline imaging time point, the long axis diameter of all target lesions is measured and recorded. A response of the target lesions is assessed by determination of the overall SOD of the lesions (SOD for that imaging time point). A response for each baseline non-target lesion is determined and recorded. The presence of any new lesions is recorded (of note a lymph node must measure at least 1.0 cm by short axis diameter to qualify as a pathologic lesion).

Target lesion response

Complete response (CR): disappearance of all target lesions. Any pathological lymph nodes (whether target or non-target) must have reduction in short axis to < 10 mm.

Partial response (PR): At least a 30% decrease in the SOD of target lesions, taking as reference the baseline SOD.

Progressive disease (PD): At least 20% increase in the SOD of target lesions, taking as reference the smallest prior SOD in the trial (this includes the baseline sum if that is the smallest in the trial). In addition to the relative increase of 20%, the sum must also demonstrate an absolute increase of least 5 mm.

Stable disease (SD): Neither sufficient shrinkage to qualify for PR nor sufficient increase to qualify for PD, taking as reference the smallest SOD while in the trial.

Non-target lesion response assessment

Complete response (CR): Disappearance of all non-target lesions and normalization of tumor marker level. All lymph nodes must be non-pathological in size (<10 mm short axis).

Non-CR/Non-PD: Persistence of 1 or more non-target lesion(s) and/or maintenance of tumor marker level above the normal limits.

Progressive disease (PD): Unequivocal progression of existing non-target lesions. (Note: the appearance of 1 or more new lesions is also considered progression).

New lesion assessment

At each post-baseline imaging time point, an evaluation of the presence of new lesions (yes/no) is made. The lesions are recorded as new lesions and not target or non-target lesions.

Lymph nodes must be a new lesion and measure at least 10 mm by short diameter to qualify as a new lesion overall response assessment.

A lesion identified on a follow-up study in an anatomical location that was not scanned at baseline is considered a new lesion.

Overall response assessment

Overall response assessment is based on target lesion response, non-target lesion response and new lesions and is listed in [Table 1](#) below.

Table 1: Overall Response Definitions Using RECIST v1.1

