9.6 Efficacy Analyses

Response of lesions and disease status will be assessed using standard RECIST v1.1 for the primary evaluation of response *and a study specific modified RECIST v1.1 referred to as immune related-RECIST v1.1 (irRECIST v1.1) for an exploratory evaluation (not implemented)*. Therefore, RECIST v1.1 will be used with the following adaptations (Appendix 1):

- Determination of progressive disease (PD) requires a confirmation of PD by imaging ≥ 4 weeks later. In order to confirm PD, both the initial lesion assessment and lesion assessment on the confirmatory scan must meet PD criteria ($\geq 20\%$ increase in sum of diameters).
- Continued treatment while awaiting radiologic confirmation of progression is encouraged if the patient is stable.

Patients that are deemed clinically unstable are not required to have repeat imaging for the confirmation of PD.

Objective response rate (ORR) and disease control rate (DCR) will be evaluated for injected and non-injected lesions as well as for all target lesions. The ORR will include patients with complete response (CR) or partial response (PR). The DCR will include patients with CR, PR, or stable disease. The ORR and DCR will be determined by Investigator using RECIST v1.1.

Unless otherwise specified, all efficacy analyses will be performed by:

- Lesion type – injected, non-injected lesions, all target lesions

- Evaluation criteria – RECIST v1.1
- Study Phase – Phase 1 by dose groups, Phase 2 by analysis groups

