APPENDIX 1 RECIST V1.1**Response Definition**

Assessments will use RECIST 1.1 guidelines, which are included in the Study Reference Manual, and study specific modification of the RECIST 1.1 guidelines referred to as immune related RECIST 1.1 (irRECIST 1.1).

RECIST 1.1

Baseline selection of lesions

All lesions are measured by long axis and short axis (perpendicular to the long axis). At baseline, all tumor lesions are identified as either target lesions or non-target lesions and will be evaluated at baseline and every post baseline imaging timepoint.

Target lesions: Minimal size of 1.0 cm by long axis unless a lymph node which must be a minimal size of 1.5 cm by short axis. Superficial lesions must measure at least 10 mm in long diameter and be measurable by calipers to qualify as target lesions. Maximum target lesions are 5 with a maximum of 2 lesions per organ representative of all involved organs.

Non-target lesions: Radiographically visible but do not meet size qualification of target lesions. Lymph nodes must measure at least 1.0 cm by short diameter to qualify as non-target lesions (if smaller considered non-pathologic). Excess target lesions (> 5 overall or 2 per organ) are followed as non-target lesions.

Baseline measurement of lesions

At baseline, the sum of the long diameters of all target lesions (5 lesions total with maximum of 2 lesions per organ representative of all involved organs), is calculated. The sum is referred to as the sum of diameters (SOD) for the baseline timepoint. All other lesions should be identified as non-target lesions and be recorded at baseline.

Postbaseline radiographic response assessment

At each post baseline imaging timepoint, the long axis diameter of all target lesions are measured and recorded. A response of the target lesions is assessed by determination of the overall SOD of the lesions (SOD for that imaging timepoint). A response for each baseline non-target lesion is determined and recorded. The presence of any new lesions are recorded (of note a lymph node must measure at least 1.0 cm by short axis diameter to qualify as a pathologic lesion).

Target lesion response

Complete response (CR): disappearance of all target lesions. Any pathological lymph nodes (whether target or non-target) must have reduction in short axis to < 10 mm.

Partial response (PR): At least a 30% decrease in the sum of diameters of target lesions, taking as reference the baseline sum of diameters.

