Progressive disease (PD): At least 20% increase in the sum of diameters of target lesions, taking as reference the smallest prior sum of diameters in the trial (this includes the baseline sum if that is the smallest in the trial). In addition to the relative increase of 20%, the sum must also demonstrate an absolute increase of least 5 mm.

Stable disease (SD): Neither sufficient shrinkage to qualify for PR nor sufficient increase to qualify for PD, taking as reference the smallest sum of diameters while in the trial.

Non-target lesion response assessment

Complete response (CR): Disappearance of all non-target lesions and normalization of tumor marker level. All lymph nodes must be non-pathological in size (<10 mm short axis).

Non-CR/Non-PD: Persistence of 1 or more non-target lesion(s) and/or maintenance of tumor marker level above the normal limits.

Progressive disease (PD): Unequivocal progression of existing non-target lesions. (Note: the appearance of 1 or more new lesions is also considered progression).

New lesion assessment

At each post baseline imaging timepoint, an evaluation of the presence of new lesions (yes/no) is made. The lesions are recorded as new lesions and not target or non-target lesions.

Lymph nodes must be a new lesion and measure at least 10 cm by short diameter to qualify as a new lesion overall response assessment.

A lesion identified on a follow-up study in an anatomical location that was not scanned at baseline is considered a new lesion.

Overall response assessment

Overall response assessment is based on target lesion response, non-target lesion response and new lesions and is listed in Figure 1 below.

Figure 1: Overall Response Definitions Using RECIST 1.1

Target Lesions	Non-target Lesions	New Lesions	Overall Response
CR	CR	No	CR
CR	Non-CR/non-PD	No	PR
CR	Not evaluated	No	PR

PR	Non-PD or not all evaluated	No	PR
SD	Non-PD or not all evaluated	No	SD
Not all evaluated	Non-PD	No	NE
PD	Any	Yes or No	PD
Any	PD	Yes or No	PD
Any	Any	Yes	PD

CR = complete response; NE = not evaluable; PD = progressive disease; PR = partial response; SD = stable disease.

Approved

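### SAP Appendix 1 sets the size at which a new lymph node counts as a new lesion at 10 cm, where Protocol Appendix 6 and the rest of the SAP appendix use 10 mm

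*SAP*

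**What the plan says.** SAP Section 9.6 points to Appendix 1 for the RECIST v1.1 criteria behind the efficacy analyses. Under New lesion assessment, that appendix requires lymph nodes to "measure at least 10 cm by short diameter to qualify as a new lesion". The SAP text appears twice in the published file, and the sentence is the same in both copies.

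Protocol Appendix 6 has the same sentence with a different unit: "Lymph nodes must be a new lesion and measure at least 10 mm by short diameter".

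Elsewhere, SAP Appendix 1 agrees with the protocol. Its paragraph on post-baseline assessment, where it describes recording new lesions, notes that "a lymph node must measure at least 1.0 cm by short axis diameter to qualify as a pathologic lesion". Its rule for non-target complete response reads "All lymph nodes must be non-pathological in size (<10 mm short axis"). It also uses 1.0 cm short diameter as the lower limit for a non-target node.

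Two further statements show what the threshold does. The appendix notes that "the appearance of 1 or more new lesions is also considered progression". It also says of new lesions: "The lesions are recorded as new lesions and not target or non-target lesions". On who makes the assessment, SAP Section 9.6 states: "The ORR and DCR will be determined by Investigator using RECIST v1.1".

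**The concern.** The sentence decides whether a new node counts as a new lesion, and a new lesion alone makes the overall response PD. A node counted under the protocol and ignored under the SAP would give the same patient two different responses at the same scan. ORR is the Phase 2 primary endpoint. The SAP also keeps DCR, duration of response and PFS, all of which depend on when PD is called. The SAP contains both 1.0 cm and 10 cm and does not say which prevails.

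**Working it through.** No power or sample-size figure is involved. The check compares the passages, converts one unit and traces the consequence through the response table.

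**1. Node thresholds side by side (short axis)**

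| Source | Purpose | Threshold | In mm |
|---|---|---|---|
| Protocol Appendix 6, New lesion assessment | node counts as new lesion | 10 mm | 10 |
| SAP Appendix 1, New lesion assessment | node counts as new lesion | 10 cm | 100 |
| SAP Appendix 1, post-baseline assessment | node is pathologic | 1.0 cm | 10 |
| SAP Appendix 1, non-target lesions | node qualifies as non-target | 1.0 cm | 10 |
| SAP Appendix 1, non-target CR | node is non-pathological | below 10 mm | below 10 |

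Ratio: 100 mm / 10 mm = 10. The range in dispute runs from 10 mm to just under 100 mm.

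**2. Through the SAP response table**

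Take a new node in that range, with no non-target progression.

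| Target lesions | New lesion at 10 mm | Overall response | New lesion at 10 cm | Overall response |
|---|---|---|---|---|
| PR | Yes | PD | No | PR |
| SD | Yes | PD | No | SD |

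New lesions are kept out of the target and non-target sets. Read literally, no other line of the table would turn that node into PD.

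**3. Which endpoints could move**

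- ORR: only if the node appears at or before the scan that would otherwise be the first response. A node that appears after a response leaves ORR unchanged, because SAP Section 9.6.1 counts patients who achieve CR or PR.
- DCR: by the same reasoning, only if no stable disease or better was recorded before the node appeared.
- Duration of response: a later node could end the response later, or not at all, under the 10 cm reading.
- PFS: possible, but SAP Section 9.6.6 counts confirmed PD or death. Section 9.6 asks for a repeat scan at 4 weeks or later and describes the PD criterion on both scans as a rise of 20% or more in the summed diameters. Patients judged clinically unstable need no repeat scan. Taken as literally as the 10 cm, that rule may leave progression by a new node alone unconfirmed at either threshold.

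**4. Size per reclassified patient**

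Planned group of about 25: 1/25 = 4.0 points. Group of about 50: 1/50 = 2.0 points. SAP Section 2.0 reports pooled analysis groups rather than protocol cohorts. The 2 mg melanoma-experienced group takes in Cohort 8 (about 50 planned) plus others, so one patient moves it by at most about 2 points. The SAP splits Cohorts 1 to 4 by dose without giving the split, so exact group sizes cannot be derived.

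**The case against.** The strongest reply is that this is an evident unit slip with no practical consequence. Investigators determine response, and they worked from the protocol (10 mm) and the RECIST guideline in the Study Reference Manual. The SAP is dated 4 November 2019 and is an analysis document. New lesions are recorded as yes or no, and neither document describes applying a size cut-off at analysis. The rest of the SAP appendix points plainly to 10 mm. In addition, Amendment 9 made Protocol Appendix 6 informational.

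Most of this stands, and it limits the consequence. A reader might infer that the SAP will miss nodal progression and overstate response, disease control and PFS. The documents do not support that: nothing shows that 10 cm was ever applied to a patient, and the confirmation rule separates a new node from a PFS event. A reader might also take 4 points per patient as general, but it fits only groups near 25. Nor is this an arithmetic error, since no calculation in the plan is wrong.

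The reply does not make the sentence harmless. SAP Section 4.0 leaves a central imaging laboratory for endpoint determination to the sponsor's decision. SAP Section 9.6 asks for results by injected, non-injected and all target lesions. A central read, derivation or check built on Appendix 1 would meet the wrong number. Amendment 9 does not remove the issue either. Protocol Section 8.2.1.1 still allows ORR and DCR on data collected before it, and the SAP, written to Amendment 8, keeps all these endpoints.

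**Conclusion.** The point holds as an inconsistency in a decision threshold. SAP Appendix 1 states 10 cm where Protocol Appendix 6 and the other node-size statements in the same appendix give 10 mm, a ten-fold difference. That the SAP is wrong as written is certain from the text.

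Any effect on results is conditional. It requires that someone apply the sentence literally, that a patient have a new node of 10 to 99 mm, that nothing else make the response PD at that scan and, for ORR, that the node appear at or before the first response. The size is about 4 points per reclassified patient in an analysis group of about 25, and less in the larger pooled melanoma groups. These figures rest on planned numbers. The documents give no count of such nodes, so no overall bias can be estimated. The correction should be made, but there is no basis for saying that reported results are wrong.

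**What to change.** In SAP Appendix 1, New lesion assessment, change 10 cm to 10 mm in both copies of the text, and record the change in the SAP revision history (Section 10.0). The sentence then agrees with Protocol Appendix 6 and with the rest of the SAP appendix. If any central read, response derivation or data check was specified from Appendix 1, confirm that it used 10 mm.

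The text change is a single unit. It alters no sample size, power statement, data collection or patient procedure.

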1.0 INTRODUCTION

This statistical analysis plan contains definitions of analysis populations and endpoints, outlines the timing of statistical analyses, and provides a comprehensive description of statistical analyses to be implemented to assess the safety, tolerability, biologic activity, and preliminary efficacy of SD-101 in combination with pembrolizumab as described in Protocol DV3-MEL-01 (Amendment 8: 08 February 2018): “A Phase 1b/2, Open-label, Multicenter, Dose escalation and Expansion Trial of Intratumoral SD-101 in Combination With Pembrolizumab in Patients With Metastatic Melanoma or Recurrent or Metastatic Head and Neck Squamous Cell Carcinoma (HNSCC)”.

Due to strategic changes, only some of the objectives will be evaluated. Those objectives not evaluated will be *italicized* and annotated as “*(not implemented)*”, where applicable, throughout this SAP; statistical methods for these objectives are also not described. The main text of this SAP covers only assessment of the objectives by data contained in the clinical database. Pharmacodynamic assessment will be described in an annex to this SAP. Pharmacodynamic objectives will also be annotated.

Groupings of patients to be used in the analyses are also changed from what were described in the protocol, based on the knowledge accumulated through the conduct of the trial.

2.0 STUDY OVERVIEW

This open-label, multicenter, dose-ranging and expansion trial is designed to evaluate the safety and preliminary efficacy of intratumoral SD-101 in combination with pembrolizumab for the treatment of metastatic melanoma and HNSCC. The hypothesis to be tested in the clinical development of SD-101 is that SD-101, by virtue of its potency and its ability to induce high levels of interferons (IFNs), will have meaningful efficacy in generating anti-tumor immune responses when combined with an anti-PD-1 antibody. IFNs have multiple effects on both tumor cells and tumor-infiltrating leukocytes. These IFNs can directly inhibit the proliferation of tumor cells and increase MHC class I expression, enhancing antigen recognition. Additionally, IFNs have potent effects on tumor-infiltrating leukocytes, including enhancing the antigen presenting function of dendritic cells, increasing the effect or function of T cells, and activating cytotoxic activity of NK cells.

The rationale for treating metastatic melanoma and HNSCC with combination anti-PD-1/L1 therapy plus SD-101 is based on the unmet need to improve upon single anti-PD-1/L1 activity in these patient populations and nonclinical data (Protocol Sections 2.4 and 2.5) which suggest improved anti-tumor activity with the combination compared to anti-PD-1/L1 alone.

The study will be performed in 2 phases. The population to be studied in Phase 1 (Dose Escalation) will be patients with metastatic melanoma. The populations to be studied in Phase 2 (Dose Expansion) will be patients with metastatic melanoma and patients with

recurrent or metastatic HNSCC. In phase 1 of the study, doses of 1.0 mg, 2.0 mg, 4.0 mg, and 8.0 mg of SD-101 each in a single lesion will be tested in a modified, staggered, 3 + 3 trial design, to identify an optimal dose of SD-101 given in combination with pembrolizumab to be used in Phase 2 (see Protocol section 9.1 for DLT definitions and stopping rules). This optimal dose from Phase 1 is referred to in the protocol as the recommended Phase 2 dose (RP2D) of SD-101. Phase 2 of the study is designed to evaluate the safety and efficacy of SD-101 plus pembrolizumab in both metastatic melanoma and HNSCC patients. Tumor response will be evaluated separately for injected and non-injected lesions as well as all combined lesions in order to assess both a local and systemic response to study treatment.

The trial population includes a total of approximately 284 men and women with at least 1 site of disease that qualifies as a target lesion per RECIST v1.1 and is accessible for intratumoral injection.

Phase 1 Dose Escalation Cohorts 1-4 will include up to 24 patients with metastatic melanoma who are anti-PD-1 naïve or experienced.

Phase 2 Dose Expansion will include approximately 160 patients with metastatic melanoma and approximately 100 patients with recurrent or metastatic HNSCC:

- 1) Expansion Cohort 1 of approximately 60 melanoma patients who are anti-PD-1/L1 naïve
- 2) Expansion Cohort 2 of approximately 25 melanoma patients who have disease progression on anti-PD-1/L1 therapy
- 3) Expansion Cohort 3 of approximately 25 HNSCC patients who are anti-PD-1/L1 naïve
- 4) Expansion Cohort 4 of approximately 25 HNSCC patients who have disease progression on anti-PD-1/L1 therapy
- 5) Expansion Cohort 5 of approximately 25 melanoma patients who are anti-PD-1/L1 naïve
- 6) Expansion Cohort 6 of approximately 25 HNSCC patients who are anti-PD-1/L1 naïve
- 7) Expansion Cohort 7 of approximately 25 HNSCC patients who are refractory or resistant to anti-PD-1/L1 therapy
- 8) Expansion Cohort 8 of approximately 50 melanoma patients who are refractory or resistant to anti-PD-1/L1 therapy.

Some of these study groups will be rearranged for final analysis as analysis groups based on tumor indications, anti-PD-1/L1 experience, and dose of SD-101.

Phase 1 results will be presented for each of the 4 dose groups.

Results for Phase 2 objectives, using combined Phases 1 and 2 data, will be presented by 2mg/lesion and 8mg/lesion doses for

- MEL/NAIVE: metastatic melanoma patients who are anti-PD-1/L1 naïve, including
 - subjects in Phase 1 2mg and 8mg groups
 - subjects in Phase 2 Cohort 1 (both 2mg/lesion and 8mg single lesion) and Cohort 5 (2mg/lesion)
- MEL/EXP: metastatic melanoma patients who are anti-PD-1/L1 experienced, including
 - subjects in Phase 1 2mg and 8mg groups
 - subjects in Phase 2 Cohort 2 (both 2mg/lesion and 8mg/lesion) and Cohort 8 (2mg/lesion)
- HNSCC/NAIVE: HNSCC patients who are anti-PD-1/L1 naïve, including
 - subjects in Phase 2 Cohort 3 (both 2mg/lesion and 8mg/lesion) and Cohort 6 (2mg/lesion)
- HNSCC/EXP: HNSCC patients who are anti-PD-1/L1 experienced, including
 - subjects in Phase 2 Cohort 4 (both 2mg/lesion and 8mg/lesion) and Cohort 7 (2mg/lesion)

2.1 Phase 1

Patients in Escalation Cohorts 1-4 will be administered 1.0 mg, 2.0 mg, 4.0 mg, and 8.0 mg, respectively, of SD-101 in combination with 200 mg pembrolizumab Q3W per the Schedule of Trial Events (see Protocol Section 4.1.1 for dosing schema).

2.2 Phase 2

Melanoma Dose Expansion cohorts in Phase 2 will be treated with 8.0 mg or 2.0 mg of SD-101 from Phase 1 in combination with 200 mg pembrolizumab Q3W (see Protocol Section 4.1.2 for dosing schema).

HNSCC Dose Expansion cohorts in Phase 2 will be treated with the selected RP2D (8.0 mg or 2.0 mg of SD-101) from Phase 1 in combination with 200 mg pembrolizumab Q3W (see Protocol Section 4.1.2 for dosing schema).

3.0 STUDY OBJECTIVES

3.1 Phase 1 (Dose Escalation: Metastatic Melanoma)

3.1.1 Primary Objectives

- To assess the safety and tolerability of escalating intratumoral doses of SD-101 in combination with intravenous pembrolizumab in patients with metastatic melanoma
- To evaluate the expression of IFN-inducible genes in whole blood 24 hours after intratumoral injection of SD-101 given with pembrolizumab in patients with metastatic melanoma as a pharmacodynamic marker of SD-101 activity (pharmacodynamic)
- To determine a RP2D of SD-101 in combination with pembrolizumab to be evaluated in Phase 2

3.1.2 Exploratory Objectives

- To assess the preliminary response both locally and systemically including:
 - *Treatment response of the injected Lesion A (local response) (not implemented)*
 - *Treatment response of the non-injected lesion(s) (systemic response) (not implemented)*
 - Treatment response of all lesions
 - *Time to response (not implemented)*
 - To assess changes in tumor biomarkers (pharmacodynamic)

3.2 Phase 2 (Dose Expansion: Metastatic Melanoma or Recurrent or Metastatic Head and Neck Squamous Cell Carcinoma)

